# BILICAM CLINICAL VALIDATION STUDY INVESTIGATIONAL PLAN

## A. PURPOSE

A clinical validation study will be conducted on the BiliCam system, a non-invasive technology to estimate total serum bilirubin (TSB) levels in newborn infants. The technology is based on analysis of digital images obtained using the BiliCam app installed on a commodity smartphone. The purpose of the clinical validation study is to demonstrate that the accuracy of BiliCam in estimating TSB levels in newborn infants is similar to the accuracy of the predicate device, the JM-103 (Dräger Medical, Telford, PA) brand of transcutaneous bilirubinometer. The primary study outcome is the correlation between paired TSB and Bilicam-estimated (BCB) values among a racially and ethnically diverse sample of newborn infants. The performance goal for demonstrating that BiliCam has similar accuracy as the JM-103 is:

The lower limit of the 95% confidence interval (95% CI) around the calculated correlation coefficient (r) will be  $\geq 0.83$ .

This performance goal is based on the results of studies of JM-103 used to support 510(k) applications for this device (K021622, K042522). In these studies, correlations between paired JM-103 and TSB measurements ranged from 0.84 to 0.946.

Data for the clinical validation study will be collected using the BiliCam app installed on iPhone 5s smartphones. In addition, if feasible, image data on study participants will also be collected using the BiliCam app installed on iPhone 7 phones. The data obtained with the iPhone 7 phones will be used for algorithm development and testing. Note that no BCB value will be returned to the iPhone 7 during this study as the data is being collected for research and development purposes.

## B. PROTOCOL

### **B-1.0 Scientific rationale**

Neonatal jaundice is an almost ubiquitous condition. It is estimated that 60-84% of newborns develop visual jaundice in the first few days of life. Systematic assessment to identify newborns with significant hyperbilirubinemia is a central focus of care during the birth hospitalization in the US. In a study conducted by the Better Outcomes through Research for Newborns (BORN) network, respondents from 86% of 60 newborn nurseries across the US reported that they screened virtually all neonates with either a transcutaneous bilirubin (TcB) or TSB measurement prior to discharge. Since TSB levels are the “gold standard,” and used to determine clinical care, there are advantages in using TSB screening in newborn nurseries. TcB measurement is a non-invasive technology to screen newborns for jaundice using a hand-held portable device. Although not as accurate as TSB measurement, there are several validated decision rules for using TcB measurements to determine which newborns need a blood draw for a TSB level; use of TcB screening and these screening rules can obviate the need for a blood draw in 80% - 90% of neonates during their birth hospitalization. TcB measurement also has an advantage in that, because it is a portable and non-invasive methodology, it is easy to perform serial measurements on an infant and the results are virtually instantaneous. Thus, either TSB or TcB screening is an effective method to identify jaundiced newborns during their newborn nursery stay.

Unfortunately, bilirubin levels typically peak in neonates around 96 hours of life, well after most infants are discharged from the newborn nursery. Because of this, the American Academy of Pediatrics (AAP)

recommends that newborns discharged before 72 hours of age be seen by a healthcare provider within the subsequent 48-72 hours to assess for jaundice. However, accurate assessment of the severity of jaundice in outpatient neonates is problematic. TSB measurement is more difficult in newborns after discharge than it is during the birth hospitalization. TcB measurement would be a viable option, however, TcB meters are not in wide use in outpatient settings, likely because each TcB meter costs thousands of dollars. Given these obstacles, the outpatient assessment of jaundice in neonates is generally done by visual inspection of an infant's skin to assess the degree of yellowness. However, while both parents and clinicians are usually able to identify the presence of jaundice, there is ample evidence that even experienced healthcare providers cannot accurately estimate its severity. In studies comparing visual assessment of jaundice with TSB levels, correlation coefficients are in the 0.36 - 0.75 range, with poor inter-observer agreement. Most concerning are data that indicate that, when using visual assessment, clinicians frequently underestimate the severity of jaundice.

In resource-poor areas, kernicterus continues to be a major, and underappreciated, source of neonatal morbidity and mortality. There are ~500,000 newborns each year born in low- and middle-income countries who develop "extreme hyperbilirubinemia" (EHB) leading to 114,000 neonatal deaths and 75,000 cases of kernicterus. A primary reason for these depressing statistics is the lack of ability to measure bilirubin levels in many locations, particularly now that low-cost phototherapy units have been developed.

There is clearly a global need for an inexpensive and widely available technology that could be used by physicians, nurses, other healthcare workers and parents to screen newborns for jaundice. Based on this need, a group of faculty and staff from the University of Washington developed BiliCam, a technology based on the analysis of digital images obtained with a smartphone app to provide an estimate of TSB.

A detailed description of BiliCam is provided in section D. Briefly, the BiliCam app is designed to obtain images of a portion of a newborn's skin in a standardized manner using a commodity smartphone and transmit the image data via the internet to a computer server for analysis. The process of obtaining a set of Bilicam images is initiated by placing a color calibration card (a modified Macbeth Color Checker in the shape of a hollow square) on the newborn's sternum. This card helps to both account for variations in lighting conditions and facilitate image capture and data extraction. The user starts the app and a red square appears on the smartphone screen. When this square is properly aligned with the color calibration card and lighting is adequate, the app automatically captures images using the smartphone camera; both a flash and ambient lighting image are obtained. The square of the viewfinder becomes smaller directing the user to move further from the newborn and the process is repeated. Ultimately, a set of 6 images, both flash and non-flash images at each of 3 distances from the newborn, are obtained. The user then "submits" the images to a cloud-based server.

At the server, the red, green and blue (RGB) values of pixels from multiple regions of the color calibration card and from an area of the newborn's skin in the "hollow" portion of the card are measured; these measurements are also transformed into additional color spaces. A set of these color measurement values, or "features", are entered into an algorithm used to calculate a bilirubin value. This estimated bilirubin level is then transmitted back to the smartphone.

### **B-1.1 Preliminary study**

Between October 2014 and July 2016 a preliminary study of BiliCam was conducted. The goals of the preliminary study were two-fold: 1) estimate the accuracy of BiliCam in estimating bilirubin levels in a racially and ethnically diverse sample of newborns, and 2) develop a specific algorithm for converting image data into the estimated bilirubin level. For the study, data on paired TSB values and BiliCam-estimated bilirubin levels

were collected on a racially and ethnically diverse sample of 530 newborns from 7 institutions across the US using the BiliCam app installed on an iPhone 5s. Data were collected on newborns both during their birth hospitalization and in outpatient settings. TSB values ranged from 0.6 mg/dL to 24.8 mg/dL.

[figure not shown]
Using a 10-fold cross validation procedure to provide an unbiased assessment of accuracy, the correlation between estimated bilirubin levels and the matching TSB value was 0.91 (95% confidence interval [95% CI] 0.89, 0.92). As summarized in the table below, BiliCam worked well in newborns with a variety of skin pigmentation.

**Table. Correlation between BiliCam-estimated bilirubin (BCB) levels and TSB levels in newborns from different racial and ethnic groups.**

Group	Number	Correlation coefficient
All	530	0.91
White	293	0.92
African American/Black	110	0.90
Asian	112	0.88
Hispanic/Latino ethnicity	139	0.91

The mean difference between the estimated bilirubin level and TSB was 0.01 mg/dL  $\pm$  1.8 mg/dL, with a range of -5.1 mg/dL to +6.4 mg/dL. A Bland-Altman plot summarizing the differences between BCB and TSB is shown below; the limits of agreement were -3.6 mg/dL to +3.6 mg/dL.

**Figure. Bland-Altman plot of differences between BiliCam-estimated bilirubin (BCB) levels and TSB levels.**

TcB measurements were made on a subgroup of 331 study newborns. In these infants the correlation between TcB and TSB was 0.91 (95% CI 0.90, 0.93). The mean TcB-TSB difference was 0.51 mg/dL  $\pm$  1.8 mg/dL, with a range of -4.6 mg/dL to +5.9 mg/dL; the limits of agreement were -3.2 mg/dL to +4.2 mg/dL.

The results from this study suggest that BiliCam has comparable accuracy to TcB, both from the data collected on TcB measurements in the project and in other published studies. In previous studies, the correlation coefficients between TcB and TSB have ranged from 0.77 – 0.93. In a study that included data on 925 matched TcB and TSB levels in babies at 27 newborn nurseries across the US, the mean TcB – TSB difference was 0.84 mg/dL  $\pm$  1.78 mg/dL, and the range of differences was -6.9 mg/dL to 8.8 mg/dL. The correlation between paired measurements was 0.78.

In addition to assessing the accuracy of BiliCam, the study data were used to develop a “locked down” algorithm for converting image data into an estimated bilirubin level. The algorithm resides on the server, where the estimated bilirubin level is determined. This estimated level is then transmitted via the internet back to BiliCam app on the user’s smartphone.

Overall, BiliCam has the potential to revolutionize the management of neonatal jaundice. During the birth hospitalization, BiliCam could provide a less expensive and more widely available technology to screen newborns for hyperbilirubinemia. For clinicians (physicians, nurses, nurse midwives, lactation consultants) in outpatient settings, BiliCam could be an effective tool for determining which newborns require a blood draw for a TSB level. In addition, because of its low cost and wide availability, in low- and middle-income countries BiliCam might become part of a system of care that could save thousands of lives annually by identifying jaundiced newborns before they develop kernicterus and prevent significant morbidity from EHB.

## **B-2.0 Study procedures**

A prospective study will be conducted at a minimum of 3 sites comparing paired TSB and BiliCam-estimated bilirubin (BCB) levels in a racially and ethnically diverse sample of newborn infants.

### Inclusion criteria

- Age < 192 hours
- Born at  $\geq$  35 weeks gestation
- Parent provides written informed consent for child to participate
- Parent speaks and reads English

### Exclusion criteria

- Previous or ongoing treatment with phototherapy for hyperbilirubinemia
- Medical or other complications that preclude completion of the study as determined by the principal investigator at each study site

## **B-2.1. Sample size**

It is planned to have 225 subjects complete study procedures, defined as having blood drawn for a TSB level and valid BiliCam images obtained, with the goal of collecting data on  $\geq$  200 newborns who have paired BCB and TSB data available for the primary analyses. As described in section B-2.2, at each study site, one of two enrollment plans will be used: “Simultaneous” (in which enrollment and the study visit will occur at one time-point), or “Staged” (in which the study visit occurs at a later time from enrollment). At sites using the Staged enrollment plan, a proportion of subjects who are enrolled will not complete study procedures because: 1) they

become ineligible because of the occurrence of an exclusion criterion after enrollment, but before the study visit occurs, 2) parents withdraw consent, or 3) subject does not return for the study visit. At these sites, up to 150 subjects will be enrolled and enrollment will be discontinued when a maximum of 75 newborns at the site have completed study procedures. At sites using the Simultaneous enrollment plan, because all subjects are expected to have completed study procedures, up to a maximum of 75 subjects will be enrolled.

## **B-2.2. Enrollment plan**

The goal of the enrollment plan is to obtain data on newborns across the entire measuring range of BiliCam (0-20 mg/dL) while oversampling newborns with high TSB levels. The use of two enrollment plans will enable this distribution. At sites using the Simultaneous enrollment plan, newborns will be enrolled at the time (within 2 hours) that blood is being obtained for a TSB level because the newborn is clinically jaundiced (i.e. the TSB is being ordered for clinical purposes). Thus, enrollment and the study visit will occur simultaneously. At Staged enrollment plan sites, subjects will be enrolled prior to being 48 hours old; these subjects will have a study visit after they are 48 hours old (i.e. the enrollment and the study visit will occur at different times). For these subjects, blood will be obtained for a TSB level as part of the study at the study visit.

A subject will be considered to be enrolled in the study once the consent is signed by his/her parent. Once enrolled, a subject's participation will be documented on the study case report forms and the subject will be included in the analyses of study data.

Enrollment procedures are described in detail below.

### **B-2.2.1- Simultaneous enrollment plan procedures**

Subjects who are age-eligible and are either inpatients or being seen for outpatient visit (by a lactation consultant or other provider) are eligible for enrollment. On a daily basis, the site research assistant will review the medical records of healthy newborns who are hospitalized for routine post-birth care. The research assistant will identify those newborns who meet inclusion and exclusion criteria, and who have had blood drawn within the previous 2 hours or have an order for a blood draw for a TSB level. The research assistant will approach the parent(s) of an eligible hospitalized newborn after discussion with a healthcare provider (e.g. nurse) who is caring for the newborn to ensure that it is a good time to approach the family (e.g., the mother is stable medically, not sleeping, etc). The research assistant will discuss the study with the parent(s) of an eligible newborn and, if the parent(s) is interested in participating, have the parent(s) read and sign the informed consent form.

At the time that the parent signs the informed consent form, a new study file will be opened.

Each file has a unique study ID number assigned. The research assistant will record the subject's medical record number next to the assigned study ID number on the **Site Enrollment Log**. The research assistant will also record the date that the informed consent form was signed. The signed consent form will be put in the appropriate study file. (The **Site Enrollment Log** and study case report forms are included in appendix 1).

After the consent form has been signed, the research assistant will ask the parent(s) to complete the **Parent Enrollment Form**, providing the sex, race and ethnicity of the newborn. (The **Parent Enrollment Form** is included in appendix 1). The research assistant will also obtain the enrolled subject's date and time of birth from the subject's medical record. The research assistant will complete the **Subject Enrollment Case Report Form**, which includes the subject's, sex, race and ethnicity (abstracted from the **Parent Enrollment Form**), and date and time of birth. In addition, the research assistant will confirm on the **Subject Enrollment Case Report Form** that the subject was born at  $\geq 35$  weeks gestation (based on review of the subject's medical record) by checking the appropriate box on the form.

Age-eligible newborns being seen for outpatient follow-up are also eligible for enrollment. On a daily basis the research assistant will review the list of newborns being seen by a lactation consultant or other provider. The research assistant will identify newborns who meet inclusion/exclusion criteria and who have either had blood obtained for a TSB level < 2 hours previously or have an order to have blood drawn for a TSB level because of clinical jaundice. After discussion with the provider to ensure that an identified newborn is suitable for enrollment, the research assistant will discuss the study with the parent(s) of the eligible newborn and, if the parent(s) is interested in participating, have the parent(s) read and sign the informed consent form. The research assistant will complete the **Site Enrollment Log**, have the parent(s) complete the **Parent Enrollment Form**, and complete the **Subject Enrollment Case Report Form** as described above.

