#### B-2.3. Procedures for the study visit

Study visits will occur simultaneously with enrollment at sites using the Simultaneous enrollment plan and at a later time for subjects enrolled at sites using the Staged enrollment plan. At the beginning of the study visit at all sites, the research assistant will confirm on the **Study Visit Case Report Form** that the subject does not have any exclusions for participation. Specifically, the research assistant will check the appropriate boxes on the CRF to verify that the subject: 1) is <192 hours old, 2) has not received phototherapy for treatment of hyperbilirubinemia, and 3) that the patient has not been excluded by the site PI. After confirming that the subject is eligible, the research assistant will obtain a series of images using the BiliCam app installed on the iPhone 5s assigned to the study.

Once the research assistant has obtained image data on a study participant using the BiliCam app installed on the iPhone 5s, additional image data (the same series of images) will be obtained using the BiliCam app installed on the iPhone 7 assigned to the study, if possible. At the discretion of the research assistant, these additional images may not be acquired if not practically possible (e.g. the newborn has become too fussy). The procedures for obtaining the images with the iPhone 5s and iPhone 7 are provided in Appendix 2.

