#### B- 2.3.1 Procedures for obtaining TSB values for subjects

At sites using the Staged enrollment plan, blood will be obtained by a qualified phlebotomist on study subjects immediately before, or after, the images for the BCB are obtained (i.e. within 2 hours) and sent for assay by the clinical laboratory at each site. At these sites, some study visits will occur at the time of a clinical visit. If the clinicians evaluating the baby at the clinical visit (occurring simultaneously with the study visit) determine that a TSB level is needed for clinical purposes, a second blood sample for the study will not be obtained; the TSB level obtained for clinical purposes will be used as the study value. No blood will be obtained for study purposes at sites using the Simultaneous enrollment plan. At these sites, BiliCam images will be obtained at the time (within 2 hours) of a blood draw for a TSB level that is being obtained for clinical purposes.

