#### B -2.3.2. Completing the Study Visit Case Report Form

After obtaining the BCB result on the mobile phone assigned to the study, the research assistant will record the value, and the date and time that the images were obtained, on the **Study Visit Case Report Form**. If a BCB value was not obtained, the research assistant will record "N/A" for the result, and indicate the reason why the BCB value was not available. Possible reasons for not obtaining a BCB value include not obtaining all needed images, issues with lighting, no value downloaded to phone after images are submitted to the server, or a value reported as ">20.0," i.e. outside of measuring range of the device. The initials of the research staff who performed the BiliCam test will be recorded on the CRF.

The calibration card used for the BiliCam test will be affixed to page 2 of the **Study Visit Case Report Form** in the spot indicated on the form.

At the time that the "study" TSB level result is available from the clinical laboratory at each site on a study subject, the level (in mg/dL) will be recorded on the **Study Visit Case Report Form**. In addition, the date and time that the blood was reported as being obtained will also be recorded on the CRF. For subjects in whom the "study" TSB level is a value that was obtained for clinical purposes (including all subjects from Simultaneous enrollment plan sites and a portion of subjects at sites using the Staged enrollment plan), if more than one valid level was obtained within 2 hours of the time that the BiliCam images are obtained, the TSB level drawn closest to the time that the BiliCam images were obtained will be selected as the "study" value. On the **Study Visit Case Report Form** the research assistant will indicate whether the listed TSB value was obtained specifically for the study or for clinical purposes. If no valid TSB level is available, the research assistant will record "N/A" for the result and indicate the reason on the form. Possible reasons include a blood sample that was too hemolyzed for analysis, an inadequate sample (i.e. quantity of blood not sufficient for the assay), and parents declining a study blood draw.

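### At Simultaneous sites nothing in the main text keeps the TSB result from the research assistant until imaging is complete, so a known TSB could affect which pairs enter the primary correlation

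*Combined protocol and SAP*

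**What the plan says.** Under B-2.2.1, inpatient screening at a Simultaneous site starts from the chart: "the site research assistant will review the medical records of healthy newborns who are hospitalized for routine post-birth care". Eligible infants are those "who have had blood drawn within the previous 2 hours or have an order for a blood draw for a TSB level". The outpatient paragraph uses the same window, "who have either had blood obtained for a TSB level < 2 hours previously", although there the assistant works from a list of visits and chart review is not mentioned.

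Enrollment follows this step: "A subject will be considered to be enrolled in the study once the consent is signed by his/her parent" (B-2.2). Imaging comes next: "After confirming that the subject is eligible, the research assistant will obtain a series of images using the BiliCam app" (B-2.3). The order of imaging and blood draw is left open: "BiliCam images will be obtained at the time (within 2 hours) of a blood draw for a TSB level" (B-2.3.1).

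Under B-2.3.2 the assistant then handles the reading: "After obtaining the BCB result on the mobile phone assigned to the study, the research assistant will record the value". The assistant may instead enter N/A with a reason: "Possible reasons for not obtaining a BCB value include not obtaining all needed images, issues with lighting". The laboratory TSB goes on the same form.

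B-2.7 computes Pearson's r on evaluable subjects only, meaning those with both values. B-2.7.1 sets one pass/fail rule: the lower limit of the two-sided 95% CI must be at least 0.83.

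**The concern.** In a comparison against a reference standard, the person running the index test should not know the reference value. Here, infants whose blood is already drawn can be identified, consented and imaged after sampling, by someone whose job includes opening the record where the result would appear.

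The BCB calculation itself is protected, because it runs on a server with a locked algorithm. Several human decisions around it are not: whom to approach, whether to complete and submit a set of images, whether to repeat one, and whether to enter N/A. Each changes the set of pairs that is analysed. If a known TSB steers them towards agreement, r rises with no gain in accuracy, and the study has one correlation bound on which to pass or fail.

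The effect would also be hard to check afterwards. B-2.3.2 records the times of imaging and blood draw, but does not mention when the result was released or seen.

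**Working it through.** **1. Can the TSB be known before imaging?**
- Infant with an order and no draw yet: not at approach. Possible later, if blood is drawn before imaging.
- Infant already drawn: possible, if the laboratory reports before imaging ends. Imaging must fall within 2 hours of the draw, and consent and forms come first, so the result must return in less than 2 hours.
- The documents give no laboratory turnaround, so the frequency is unknown.

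**2. The plan's own figure.** Inputs from B-2.7.1: n = 200, true r = 0.90, bound 0.83. By Fisher's z:

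Φ[(atanh 0.90 − atanh 0.83) × √(200 − 3) − 1.96] = Φ[(1.4722 − 1.1881) × 14.036 − 1.96] = Φ(2.03) = 0.979.

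This agrees with the stated chance of more than 95%, and the sample size is not in dispute. To pass, the observed r must reach tanh(1.1881 + 1.96/14.036) = 0.869.

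**3. Share of pairs exposed.** B-2.7.1 plans 225 completers, 75 per site, so 225/75 = 3 sites. C-2.0 caps enrollment at 375, with 150 per Staged site and 75 per Simultaneous site. Since 150 + 150 + 75 = 375, the cap implies one Simultaneous site, or one third of pairs: 200/3 ≈ 67.

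**4. Illustration.** All of the following is assumed; none of it is in the documents:
- TSB SD is 4 mg/dL, and BCB equals TSB plus independent error.
- At the Simultaneous site, a given fraction of readings more than 3 mg/dL from the TSB is repeated, and the second reading replaces the first.
- Errors of the two readings correlate at 0.5.

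Error SD = 4 × √(1/r² − 1), which is 2.69 mg/dL at r = 0.83 and 1.94 at r = 0.90. At r = 0.83 the share of discordant readings is 2 × [1 − Φ(3/2.69)] ≈ 26%, or about 67 × 0.264 ≈ 18 of the exposed pairs.

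Simulated chance of passing at true r = 0.83:

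| Discordant readings repeated | Approximate number of repeats | Chance of passing |
|---|---|---|
| none | 0 | 2.6% |
| 5–10% | 1–2 | about 3% |
| 25% | 4–5 | about 4% |
| 50% | 9 | about 6% |
| 100% | 18 | about 12% |

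At true r = 0.90 the chance goes from about 98% with no repeats to over 99% with all repeated.

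**5. A second mechanism.** Suppose instead that discordant pairs are lost, for example through N/A. Losing 25%, 50% or 100% of the most discordant 10% of pairs at the one Simultaneous site gives 3.7%, 6.2% or 11.0% at true r = 0.83. The size is similar, and the loss rates are again assumed.

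**The case against.** The strongest reply is that the illustration models conduct the plan does not describe. It needs the result to be back and seen, compared with the BCB on the phone, and acted on. At a repeat rate of 5–10%, about one or two infants, the change is too small to matter. That stands, and it is why the figures serve only as a scale.

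The plan also has safeguards: automatic image capture (B-1.0), a locked server algorithm (B-1.1), the rule that the TSB nearest in time is used, N/A reasons and tester initials (B-2.3.2), incident forms (B-2.4), 100% CRF monitoring (B-2.8) and uploaded metadata for each sample (D-4.0). Ages at imaging and at blood draw reach the biostatistician (B-2.6), so pairs imaged before the draw can be found. These leave an audit trail. They do not stop a known TSB from influencing approach, submission or repetition, and pairs imaged after the draw cannot be sorted by whether the result had been seen.

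Appendix 2 holds the imaging instructions and Appendix 1 the forms. Their content was not available, and either may already settle the matter.

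A wide TSB spread raises r with or without masking, and B-2.2 openly aims to oversample high levels. That goal is not a fault. B-2.2 assigns it to the use of two enrollment plans, however, and not to choosing infants on individual results.

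Two stronger readings are tempting. A reader might infer that staff will resubmit discordant readings, or that a passing result would be unreliable; the documents show only that the route is open. A reader might also assume two Simultaneous sites of three, where the chance of passing at r = 0.83 approaches 38% if every discordant reading is repeated. Two such sites would give a cap of 150 + 75 + 75 = 300, not 375. B-2.0 says a minimum of three sites, so other mixes are possible, but that is not the planned case.

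**Conclusion.** The point holds as a gap in the written procedure. Sections B-2.2.1 to B-2.3.2 allow selection, consent and imaging after the reference sample is drawn. The main text neither delays sight of the result nor says which submission is analysed.

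The size cannot be fixed from the documents. Under the stated assumptions, with one third of pairs exposed, the chance that a device with true r = 0.83 passes rises from 2.6% to somewhere between about 3% and 12%, depending on an unknown repeat rate. If the device performs as planned (r = 0.90), the decision hardly changes. The matter is therefore important only if true performance lies near the bound. It is worth correcting because the correction costs little and the exposure cannot be reconstructed later.

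**What to change.** - In B-2.2.1 and B-2.3, require that images are submitted and the BCB recorded before the research assistant views the TSB result. If an appendix already says so, cite it there.
- Add a Study Visit CRF item: *TSB result known before imaging (Y/N)*.
- In B-2.3.2 and B-2.7, state that the analysed BCB is the first valid submission, checked against the server record. This also covers a result that arrives between a first and a second set of images.
- In B-2.7, add a sensitivity analysis of the primary correlation that omits pairs where the TSB was known.

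The cost is a few sentences, one CRF item and one extra analysis. Sample size, endpoint and acceptance criterion stay as they are. The downside is that staff must check draw orders and times without opening results, and the sensitivity analysis will have fewer pairs and a wider interval.
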